4. STATISTICAL METHODS

4.1. Sample Size Justification

The sample size for this study will be 120 randomized subjects to accommodate for dropouts and based on the rationale that follows.

For this trial, conservatively assuming a TRUE underlying difference between treatments of 1.24 units and pooled SD=2.01, N=112 (56/group) has ~90% power to yield a statistically significant (alpha=0.05, 2-sided) difference between treatments in change from baseline to Week 8 in the total SARA score. This calculation is via 2-sample t-test, which is likely conservative compared to the planned repeated measures analysis planned for this trial to leverage the likely correlation of response between Weeks 4 and 8.

4.2. General Statistical Methods and Data Handling

4.2.1. General Methods

All output will be incorporated into Microsoft Excel or Word files, sorted and labeled according to the International Conference on Harmonization (ICH) recommendations, and formatted to the appropriate page size(s).

Tabulations will be produced for appropriate demographic, baseline, efficacy,

safety, and other parameters. For categorical variables, summary tabulations of the number and percentage within each category of the parameter will be presented. If applicable, a category for missing data will also be presented. For continuous variables, n, mean, median, SD, minimum and maximum values will be presented. The median, minimum, and maximum values will be presented with the same precision as the data. The mean will be presented with the precision of the data + 1 decimal place. The SD will be presented with the precision of the data + 2 decimal places.

Formal statistical hypothesis testing and summary statistics will be presented, as well as confidence intervals on selected parameters, as described in the sections below.

4.2.2. Computing Environment

All statistical analyses will be performed using SAS statistical software (Version 9.2 or higher). Medical history and AEs will be coding using the Medical Dictionary for Regulatory Activities (MedDRA, Version 19.1). Concomitant medications will be coded using World Health Organization Drug Dictionary (WHO-DD, Sep2016).

4.2.4. Adjustments for Covariates

4.2.5. Multiple Comparisons/Multiplicity

Type 1 error will be controlled for the primary and secondary efficacy endpoints by testing them with a fixed sequence procedure. The primary endpoint, change from baseline in the total SARA score, will be tested at a two-sided alpha level of 0.05. If this test is significant, then a single secondary endpoint, PGI-C, will also be tested at a two-sided alpha level of 0.05. If the test of the primary endpoint is not significant, then the p-value for the secondary endpoint will be presented only for descriptive purposes, and no conclusions may be drawn from this result.

The multiplicity corrections discussed above apply only to analyses done on the FAS population. Any parallel analyses performed on the PP population are considered to be sensitivity analyses, and are not corrected for multiplicity.

4.2.7. Withdrawals, Dropouts, and Loss to Follow-up

Subjects who withdrew from the study were not replaced.

4.2.8. Missing, Unused, and Spurious Data

Unless otherwise noted, efficacy analyses will be based on observed data only. No missing data will be imputed. We expect the amount of data that will be lost in the 8-week double blind phase of this study to be small; most likely less than 10%.

For efficacy analyses, partial or missing dates will not be imputed. The relative study days, where determined, will be calculated for full dates only.

4.2.9. Visit Windows

The protocol-specified visit window is ± 2 days during the Randomization Phase and ± 7 days during the Extension Phase of the study. Observations collected within ± 1 week visit window during the Randomization Phase and ± 2 weeks visit window during the Extension Phase will be included in the analyses

Actual dates and times will be used for PK analysis rather than nominal days and times.

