4.3 Schedule of Assessments

Table 2. Schedule of Assessments and Events - Randomization Phase

	SCR	Baseline	Wk 4	Wk 8	2-Wk Post Last Dose (ONLY for subjects NOT entering extension phase or who discontinue early)	Additional Instruction
Visit	Visit 1	Visit 2	Visit 3	Visit 4	Visit 5	
Eligibility Assessments						
Informed Consent	Х					
Inclusion/Exclusion	Х					Should be re-reviewed at Baseline
Medical History	Х					
Demographic Assessment	Х					
Disease History	Х					
Neurological Exam	Х			Х		
Mini Mental State Exam (MMSE)	Х					
Pregnancy Test for WOCBP (serum)	X	Х		Х		
Pregnancy Test for WOCBP (urine)	^	X	Х	^		To be done within 72 hours prior to dosing at visit 2 (Baseline Visit). The site may test a patient at any time if they suspect the patient may be pregnant.
Safety Assessments						, , , , , , ,
Laboratory Assessments including						No fasting required
urinalysis	Х	Х		Х	X	ino iasting required
Serum Chemistry			х			A physician who is not the SARA rater must b available to review lab tests and manage any potential medical evaluation throughout the randomization phase
Physical Exam						PE will be done at W4 if warranted by
	Х			Х		emergence of new AE's
Physical Measurements	Х	Х	X	X		
Vital Signs	Х	Х	Х	Х		
12-Lead ECG	Х			Х		
		X	Х	Х	X	
Concomitant Medication Review	Х	^				
	X	X	X	X	X	
Concomitant Medication Review Adverse Event Assessments Sheehan Suicidality Tracking Scale (STS)	X		X	×	X	
Concomitant Medication Review Adverse Event Assessments Sheehan Suicidality Tracking Scale		х				This should be the first clinical outcome

Visit Window is +/- 2 days during the Randomization Phase

Table 3. Schedule of Assessments and Events - Extension Phase

	¹ Baseline Visit	Ext. Wk 4	Ext. Wk 8	Ext. Wk 12	Ext. Wk 24	Ext. Wk 36	Ext. Wk 48
Visit		Visit 1	Visit 2	Visit 3	Visit 4	Visit 5	Visit 6
Eligibility Assessments							
⁴ Informed Consent	Х						
Neurological Exam					Х		Х
Pregnancy Test for WOCBP (serum)	Х				Х		Х
² Pregnancy Test for WOCBP (urine)	Х	Х	Х	Х		Х	
Safety Assessments							
Laboratory Assessments including urinalysis	х				Х		Х
³ Lab: LFT tests only (ALT, AST, BILI, GGT)		х	Х	Х		Х	
Physical Exam	Х				Х		Х
Physical Measurements	V	V	V	V	V	V	V
Vital Signs	X	X	X	X	X	X	X
12-Lead ECG	X	^	^	^	X	^	X
Concomitant Medication Review	X	X	Х	X	X	X	X
Adverse Event Assessments	х	х	х	х	х	х	Х
Sheehan Suicidality Tracking Scale (Sheehan STS)	X	X	Х	Х	Х	Х	Х
* Clinical Outcome Assessment							
SARA	х		X		х	Х	Х
Clinical Drug Supply							

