6.3.1 The Scale for the Assessment and Rating of Ataxia (SARA)

The SARA was developed as a clinician-administered instrument to measure severity of symptoms in patients with SCA. While there are multiple scales available, the SARA has been tested in the most patients with SCA to date. It has been demonstrated to have excellent interrater reliability [i.e., intraclass correlations of > 0.95 (61, 62)], good test- retest reliability [intraclass coefficient of 0.90 (61)], high internal consistency [Cronbach's alpha of > 0.94 (61, 62)], sensitivity to change over time in populations with SCA (2, 63, 64) and able to detect treatment effects (65). In addition, the SARA scores were highly correlated with measures of activities of daily living, such as the Barthel Index (typically used in stroke) and the Unified Huntingtons Disease Rating Scale Part IV (typically used in Huntingtons Disease).

The SARA scores range from 0 (no ataxia) to 40 (severe). The SARA takes approximately 15 minutes to administer. Assessed items include:

[figure not shown]
- 1. Gait (rated 0 to 8)
- 2. Stance (0 to 6)
- 3. Sitting (0 to 4)

- 4. Speech disturbance (0 to 6)
- 5. Finger chase (0 to 4)
- 6. Nose-finger test (0 to 4)
- 7. Fast alternating hand movements (0 to 4)
- 8. Heel-shin slide (0 to 4)

[figure not shown]
Once each of the 8 categories has been assessed, the total score is calculated to determine the severity of ataxia. For motor activities of the four extremities (items 5-8), assessments are performed bilaterally and the mean values are used to obtain the total score.

[figure not shown]
Raters must be pre-approved by sponsor or sponsor representative (i.e. CRO) to rate

subjects on the SARA

All subjects who discontinue study treatment early should complete an Early Discontinuation Visit as well as the 2-Week Post Dose Visit. The 2-Week Post Dose Visit would not need to occur if the subject stopped taking study medication more than 2 weeks prior to the Early Discontinuation Visit. The only exception to this requirement is when a subject withdraws consent for all study procedures or loses the ability to consent freely (i.e. is imprisoned or involuntarily incarcerated for the treatment of either a psychiatric or physical illness).

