4 ANALYSIS SETS

BHV4157 cohort: Subjects that took at least one dose of BHV4157 and provided at least one post-baseline total SARA score.

- The analysis of the FAS cohort will take into account both the dosing break between phases (Randomization and Extension) and the dosing break prior to the Expanded Extension.
- The analysis of the ITT cohort will take into account the dosing break between phases (Randomization and Extension) but not the dosing break prior to the Expanded Extension.

On-treatment data for efficacy analyses are considered as any visit that occurs within 7 days (inclusive) of the post-final study treatment dose. The Final Study Visit is considered as any visit that occurs between 8 and 21 days post-final study treatment dose.

On-treatment data for safety analyses are considered as any visit or AE recorded within 30 days (inclusive) post-final study treatment dose.

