9 AD HOC ANALYSES

Additional analyses of interest not specified directly in the SAP were analyzed using the FAS. These analyses were performed on the following data cuts:

• Randomization Phase: locked data through Extension Phase Week 48

Randomization Phase

DocuSign Envelope ID: BD8AB61B-7989-408F-A5B1-B84E58727CD3

Biohaven Pharmaceuticals Protocol BHV4157-201 SAP ver 04.0 Addendum 27Mar2020

Extension Phase – Week 48

CONFIDENTIAL

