3. SUBJECT POPULATIONS

3.1. Population Definitions

The following subject populations will be evaluated and used for presentation and analysis of the data:

Full Analysis Set (FAS): All randomized subjects with at least 1 dose of study treatment and a baseline and post-baseline total SARA score during the Randomization Phase.

Per Protocol (PP) Set: All FAS subjects without any major protocol deviations.

Safety Analysis Set: All subjects who received at least 1 dose of study treatment.

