4.8.3. Laboratory Data

Clinical laboratory evaluations include:

- Hematology: hemoglobin, hematocrit, platelets, complete blood count with differential and absolute neutrophil count
- Serum Chemistry: sodium, potassium, chloride, calcium, alanine aminotransferase (ALT), aspartate aminotransferase (AST), lactate dehydrogenase (LDH), alkaline phosphatase (ALP), gamma-glutamyl transferase (GGT), phosphorous, bicarbonate, creatine phosphokinase (CPK), total protein, albumin, total bilirubin (if greater than 2 mg/dl bilirubin will be fractionated), glucose, creatinine, blood urine nitrogen (BUN), uric acid, and pregnancy testing (for women of child-bearing potential). Additionally at screening, total cholesterol, low-density lipoprotein (LDL), high-density lipoprotein (HDL), triglycerides, folate, hemoglobin A1c (HbA1C), P-Amylase, Lipase, thyroid-stimulation hormone (TSH), and T4
- Urinalysis: pH, specific gravity, protein, ketones, glucose, blood, and microscopic exam (completed only if any part of the urinalysis is not negative)
- Additional tests: human immunodeficiency virus (HIV), hepatitis B surface antigen (HBsAg), and hepatitis C virus (HCV) antibody at screening

Clinical laboratory values will be expressed using conventional units. In the event of repeat values within the same analysis visit, the measurement closest to the target day for the analysis visit interval will be used.

On-treatment laboratory abnormalities are those with an assessment date after the date/time of first dose of study drug and within 30 days after the last dose of study drug. For the Randomization Phase, treatment-emergent laboratory abnormalities will be assessed from the date of randomization until: 1) the first day of the Extension Phase or 2) if the subject did not continue into the Extension Phase, 30 days after the last dose of study drug. For the Extension Phase, treatment-emergent lab abnormalities will be assessed from the first day of the Extension Phase, treatment-emergent lab abnormalities will be assessed from the first day of the Extension Phase until 30 days after the last dose of study drug.

The observed value and change from baseline will be summarized for each continuous laboratory parameter for the Randomization and Extension Phases, separately. In addition, the shift from baseline for laboratory abnormalities (low, normal, high) will be tabulated for the Randomization and Extension Phases, separately.

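### Does the ±1-week analysis window drop early-stopper SARA ratings that the Full Analysis Set counts?

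*SAP*

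**What the plan says.** - **Who is in the set.** SAP 3.1 defines the Full Analysis Set as "All randomized subjects with at least 1 dose of study treatment and a baseline and post-baseline total SARA score during the Randomization Phase". No window or on-treatment condition is attached. Protocol 9.1 is at least as wide: one dose and one efficacy observation.
- **Which ratings are used.** SAP 4.2.9 gives the protocol's ±2-day visit window, then includes in the analyses observations within a ± "1 week visit window during the Randomization Phase". It names no target days. SAP 4.1 speaks of the correlation between Weeks 4 and 8, so those are the post-baseline visits of the model.
- **On-treatment rule.** Section 4 of the SAP addendum (March 2020) says: "On-treatment data for efficacy analyses are considered as any visit that occurs within 7 days (inclusive) of the post-final study treatment dose". A visit 8 to 21 days after the last dose is a Final Study Visit.
- **Early stoppers.** The protocol, in the text after 6.3.1, says: "All subjects who discontinue study treatment early should complete an Early Discontinuation Visit as well as the 2-Week Post Dose Visit". The second visit is waived "if the subject stopped taking study medication more than 2 weeks prior to the Early Discontinuation Visit".
- **Missing data.** Protocol 9.1 and SAP 4.2.8 impute nothing. SAP 4.2.8 expects to lose most likely less than 10% of the data in the double-blind phase.

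**The concern.** The set and the window rule use different tests. One asks whether a rating exists in the phase; the other asks whether it lies near Week 4 or Week 8. A subject who stops early and is rated between the windows passes the first test and fails the second. The Full Analysis Set could then be larger than the number of subjects behind the primary estimate.

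The on-treatment rule adds a second doubt. SAP 4.2.9 selects by calendar day, the addendum by days since the last dose. Suppose a subject takes the last dose on day 14 and is rated on day 28. The rating is inside the Week 4 window, but it is 14 days off drug, so the addendum would class it as a Final Study Visit. The visible text does not say whether the addendum's rule governs the primary model.

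What would be at stake is the data going into the one confirmatory test, which also gates the test of PGI-C (SAP 4.2.5). If subjects doing badly on active drug stopped early and their ratings were dropped, the estimate would lean toward troriluzole.

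**Working it through.** **1. The plan's own figure.** Inputs from SAP 4.1: difference 1.24, SD 2.01, 56 per group, two-sided alpha 0.05.

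- Noncentrality = 1.24 / (2.01 × √(2/56)) = 3.264, with 110 degrees of freedom and critical t 1.982. Power is 0.899, matching the stated figure of about 90%.
- With 10% of 120 lost evenly, 54 per arm remain. Noncentrality = 1.24 / (2.01 × √(2/54)) = 3.206; power is 0.888.

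**2. The windows.** Assume Week 4 is day 28 and Week 8 is day 56.

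- ±7 days gives days 21-35 and 49-63.
- Days 1-20 (20 days) and 36-48 (13 days) lie in neither, 33 of 56. Counting the first dose as day 1 moves the gaps by one day, to days 1-21 and 37-49.
- Scheduled ratings at ±2 days fall on days 26-30 and 54-58, wholly inside the windows.

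So the 33 days are days on which no SARA is scheduled. They do not measure a share of patients or of data. A rating on days 36-48 comes from a subject who should already have a Week 4 rating in the model. Only a stop before about day 21 can leave a Full Analysis Set subject with no usable post-baseline value.

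**3. Is there a rating to lose?** Protocol Table 2 has no early-discontinuation column; its only column for early stoppers is headed "2-Wk Post Last Dose (ONLY for subjects NOT entering extension phase or who discontinue early". The SARA row of that table cannot be read in the public copy. The protocol requires the early-discontinuation visit without saying that SARA is rated at it in this phase.

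**4. Bias if ratings before day 21 are left out.** The documents give no stopping times or correlations, so these are assumptions: 60 per arm, 6 stops in the active arm, none on placebo, SD 2.01, correlation ρ of 0.5 to 0.7 between any two ratings.

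- Stopping unrelated to SARA: no bias.
- The six worst early raters on active drug all stop. The shift is ρ × 2.01 × 0.1755 / 0.9, where 0.1755 is the standard normal density at its 90th percentile. This is 0.196 at ρ = 0.5 and 0.274 at ρ = 0.7, toward troriluzole.

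**5. Bias if those ratings are counted as Week 4 instead.**

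- Same worst case: simulation puts the bias near zero, about 0.01 to 0.02 toward troriluzole, if the full effect is already present at the early rating. If none is present, it is roughly 0.04 to 0.06 against.
- Stopping unrelated to SARA, no effect yet at the early rating: ρ × 0.10 × 1.24 = 0.062 at ρ = 0.5 and 0.087 at ρ = 0.7, against troriluzole. If the full effect is present, zero.

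Neither handling is better in every case. The alternative gives up the existing freedom from bias under unrelated stopping to protect against an extreme pattern of selective stopping.

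**The case for a change.** The best case for acting is that the rating probably exists. Protocol Tables 4 and 5 mark SARA at the early-discontinuation and two-week post-dose visits of the extension, so the same practice in the Randomization Phase is plausible. The protocol also foresees stops after Week 4 laboratory results (6.2.4.5). A stop on days 36-48 puts the visit 14 days later on days 50-62, inside the Week 8 window and off drug. For laboratory values the SAP does state a choice rule, that "the measurement closest to the target day for the analysis visit interval will be used", so a reader may expect one for SARA. Stating it would take two sentences.

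The plausibility stands, and so does the value of a short clarification. The step to a fault in the plan does not, for three reasons.

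- **The public text is incomplete where the rule would be.** The SAP's contents list puts section 4.6 on page 18 and 4.8 on page 28, yet little of that span can be read. The model is described in one sentence, and addendum section 10, on updates to the SAP's analyses, is blank after its opening. Silence there is not evidence of a missing rule.
- **The two selection rules do not contradict each other.** They can be applied in sequence. The addendum's wording covers efficacy analyses in general, and its introduction says that it adds detail on items the SAP did not discuss.
- **The planned output would expose the problem.** SAP 4.4 reports population sizes and withdrawals with reasons by arm, SAP 4.2.1 gives n for continuous summaries, and SAP 4.6 lists all efficacy data by subject and visit. Full Analysis Set subjects with no in-window rating can be counted from these.

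**Conclusion.** The mismatch between SAP 3.1 and 4.2.9 is real but narrow, and it does not call for a change. A population somewhat larger than the number contributing post-baseline data is an ordinary result of an observed-data analysis, and analysts handle it routinely.

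The size is small. At the SAP's 10% ceiling (12 of 120 subjects) power is about one percentage point below the planned figure. That is the cost of losing Week 8 data: a subject who stops before day 21 has no on-treatment Week 8 value under any windowing. The shift of about 0.20 to 0.27, some 16% to 22% of the 1.24 design effect, needs every stop to be among the worst raters and in one arm. It describes selective dropout and would arise equally if no early rating were taken, so it is not a measure of what the window rule costs.

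Nor is there a better primary rule to adopt. Counting early ratings as Week 4 can add 0.06 to 0.09 against troriluzole if the effect is delayed. By the time of the addendum the data in use were already "Randomization Phase: locked data through Extension Phase Week 48", so any new windowing would be post hoc.

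This rests on day 28 and day 56 as targets, on the SAP's own expectation of data loss, and on assumed correlations of 0.5 to 0.7. A low-priority question remains for the sponsor: is SARA rated at early-discontinuation or post-dose visits in this phase, how is such a rating assigned, and does the addendum's on-treatment rule reach the primary model? A count by arm of Full Analysis Set subjects with no in-window rating would help; if it is zero, the point about days 1-20 is closed.

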4.3. Planned Analyses

Data from the double-blind portion of the trial will be unblinded and analyzed after the last subject completes 8 weeks of treatment or discontinues from the Randomization Phase. Subjects who complete the Randomization Phase may be eligible for an open-label Extension Phase of the study. Data from the Extension Phase will be summarized after the last subject completes the last visit or discontinues from the Extension Phase.

4.4. Subject Disposition

A summary of subject disposition will be tabulated for all subjects by treatment group and overall for the Randomization and Extension Phases, separately, including:

- Number of subjects screened
- Number of screened subjects excluded from the study and reason for exclusion
- Number of subjects in each analysis population
- Number of subjects who entered the Randomization Phase
- Number of subjects who completed the Randomization Phase
- Number of subjects who prematurely withdrew from the Randomization Phase and reasons for withdrawal

- Number of subjects who entered the Extension Phase
- Number of subjects who completed the Extension Phase
- Number of subjects who withdrew from the Extension Phase and reasons for withdrawal

A by-subject listing of study completion information for both the Randomization and Extensions Phases, including the reason for withdrawal, if applicable, will be presented.

4.5. Demographic and Baseline Characteristics

Demographic information, medical and disease history, and Mini Mental State Exam (MMSE) results will be summarized by treatment group and overall, based on the Safety population. However, if a substantial difference exists between the number of subjects in the Safety and the FAS populations, then a separate similar summary will be provided for the FAS population.

Demographic and other baseline data will also be provided in by-subject data listings.

4.6. Efficacy Evaluation

Unless otherwise noted, all efficacy analyses will be conducted using the FAS and PP populations as outlined below. All efficacy data will be included in listings by subject, study medication, and visit (as applicable) for the Randomization and Extension phase, separately.

For the Randomization Phase, baseline is considered as the last visit prior to dosing (Visit 2 assessment); and for the Extension Phase, baseline is considered as the visit prior to Extension Visit 1:

- If less than 14 days elapsed between the Randomization and Extension Phases, then use the Visit 4 (Week 8) assessment during the Randomization Phase, or
- If 14 or more days elapsed between the Randomization and Extension Phases, then use the Repeat Baseline assessment at the beginning of the Extension Phase.

